4.5 Efficacy Secondary Outcomes (FA,PP)

Hepatotoxicity will be assessed using ALT and INR.

Descriptive summaries will be provided by treatment group and overall at each measurement time point during the treatment period (10 hours, 20 hours). Change from baseline to each of the 10 and 20 hour time points will be summarised by treatment group and overall for ALT and INR.

A graphical summary of each marker will be presented in a separate panel for each treatment group. Each will show the profile of the measurements for individual patients overlaid by the treatment group mean profile.

At each measurement time point during the treatment period (10 hours, 20 hours) ALT and INR will be analysed by treatment group and overall using the mean and 95% confidence interval. They will be compared within each dosing cohort between the PP100-01+NAC and the NAC alone patients using

¹ Note that PP100-01 is administered as a bolus and therefore cannot be stopped once the bolus has been given

the difference in means and its 95% confidence interval. The markers will be compared between each of the PP100-01 2µmol/kg, 5µmol/kg and 10µmol/kg groups and the combined NAC alone group in the same way. These analyses will be repeated using the change from baseline in ALT and INR, for absolute and relative change as appropriate.

Use of the natural log transformation of the data and the geometric mean summary statistic will be considered as appropriate in the descriptive, graphical and formal analyses of these markers.

Paracetamol level (mg/L) will be summarised descriptively and graphically by treatment group and overall at its baseline and 10 and 20hrs measurement time points in the same way as for the ALT and INR markers.

The following efficacy indicators will be summarised by treatment group and overall in the same manner as for the primary outcome analysis in Section 4.4.

- Proportion of patients with paracetamol/acetaminophen concentration >20 mg/L at 10 hrs
- Proportion of patients with paracetamol/acetaminophen concentration >20 mg/L at 20 hrs
- Proportion of patients with a 50% increase in ALT after 10 hrs, compared with baseline value
- Proportion of patients with a 50% increase in ALT after 20 hrs, compared with baseline value
- Proportion of patients who have doubled their ALT after 10 hrs, compared with baseline value
- Proportion of patients who have doubled their ALT after 20 hrs, compared with baseline value
- Proportion of patients with ALT>100 U/L at 10hrs
- Proportion of patients with ALT>100 U/L at 20hrs
- Proportion of patients with INR>1.3 at 20 hrs
- Proportion of patients with INR>1.3 at 20 hrs
- Proportion of patients with ALT>1000 U/L at any time

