4 OBJECTIVES AND ENDPOINTS

The present study is designed to determine safety and tolerability of PP100-01 (drug substance, calmangafodipir) when administered as an add-on to the 12hr NAC treatment regime. The purpose of this study is to investigate a therapeutic regimen for POD where NAC is combined with the SOD mimetic, PP100-01 in order to evaluate if reduction of the oxidative stress on the liver will be safe and well tolerated. Furthermore, the study will assess experimental biomarkers in serum/plasma such as CK18 and microRNA (MiR122), GLDH and mitochondrial DNA to find new markers that track organ injury and therefore drug efficacy.

Primary objective:

Safety and tolerability of PP100-01 add-on treatment to the 12hr NAC treatment regime in patients treated for paracetamol/acetaminophen overdose (POD) when NAC treatment is initiated before 24hrs post POD.

Secondary objective:

Determine if there is evidence of PP100-01 having efficacy with regard to treatment of paracetamol-induced liver injury by measurement of conventional clinical biomarkers and novel experimental biomarkers.

Primary outcome

Adverse events and serious adverse events.

Secondary outcomes:

Clinical observations (pulse rate, blood pressure, respiratory rate, pulse oximetry, temperature) Haematology and clinical biochemistry parameters

Experimental biomarkers in serum/plasma such as CK18 and microRNA (MiR122), GLDH and mitochondrial DNA

Incidence of hepatotoxicity between 12hr NAC arm and individual PP100-01 + NAC treatment arms Duration of hospital stay (days for the individual PP100-01 + NAC arms vs 12hr NAC arm)

There will be no follow-up visit, but patients will be followed up using their electronic records. The following data is collected 7, 30 and 90 days after randomisation: Representation to hospital (any reason), representation with liver injury, repeat overdose, death and transfer to liver transplantation unit. Any AEs or SAES identified would be recorded and reported.

Exploratory secondary outcomes will be collected to improve the design of future clinical studies:

- To determine the rate of occurrence of hepatotoxicity (defined by raised biochemical markers) in patients treated with PP100-01 and 12hr NAC administration regimens.
- To compare the incidence of anaphylactoid reactions in the co-treatment and 12hr NAC regimens in APAP poisoned patients.

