- To determine the occurrence of hepatotoxicity as determined at the end of the 12hr NAC administration regimen.
- To measure length of hospital stay in patients receiving co-treatment and 12hr NAC treatment regimens.
- Proportion of patients with a 50% increase in ALT after 10h post-treatment with NAC, compared with the admission value
- Proportion of patients with ALT>100 at 10h post-treatment with NAC
- Proportion of patients with INR>1.3 at 10h post-treatment with NAC
- Proportion of patients with paracetamol/acetaminophen concentration > 20 mg/mL

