6.2 Inclusion Criteria

- 1. Any patient with capacity admitted to hospital within 24 hrs either a single acute POD or more than one dose of paracetamol (staggered) and deemed to require treatment with NAC.
- 2. Provision of written informed consent
- 3. Males and females of at least 16 years of age

These patients will include:

a) Patients presenting within 8h of overdose who have a timed blood paracetamol concentration above the 100-line on the UK APAP overdose treatment nomogram (See Figure 1).

b) Patients presenting later than 8h who are at risk of liver injury from the reported dose ingested and have blood results confirming need for NAC

c) Patients presenting after taking a staggered APAP overdose (defined as when the overdose of APAP is taken over a period of more than 1hr)

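### The threshold indicators in SAP 4.5 do not separate patients already above the threshold before PP100-01 from those who cross it afterwards, and the ALT>1000 window has no start

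*SAP*

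**What the plan says.** SAP 4.5 opens its efficacy section with "Hepatotoxicity will be assessed using ALT and INR". Among the indicators it then lists are "Proportion of patients with ALT>100 U/L at 10hrs", "Proportion of patients with ALT>100 U/L at 20hrs", "Proportion of patients with INR>1.3 at 20 hrs" and "Proportion of patients with ALT>1000 U/L at any time". They are to be analysed like the primary outcome (SAP 4.4): exact 95% intervals per group, differences within each cohort (6 v 2), and differences between each dose group and the pooled NAC-alone patients (6 v 6).

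Protocol section 4 words its own outcomes the same way: "Proportion of patients with ALT>100 at 10h post-treatment with NAC", and an exploratory aim "To determine the rate of occurrence of hepatotoxicity (defined by raised biochemical markers". Neither document limits these lines to patients who were at or below the threshold beforehand.

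Protocol 6.2 admits staggered overdoses and "Patients presenting later than 8h who are at risk of liver injury from the reported dose ingested", provided that blood results confirm the need for NAC. The exclusions in 6.3 contain no upper limit for ALT or INR; only the anticoagulant exclusion bears on either marker.

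**The concern.** The secondary objective asks whether PP100-01 affects paracetamol-induced liver injury. A level at 10 h or 20 h mixes two kinds of patient: those whose injury was present before the bolus and those whose injury appeared after it. Only the second kind can show prevention, and the table does not tell them apart. A patient whose ALT falls from 400 to 250 (a made-up example) is counted above 100 at both times, although improving.

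The any-time ALT>1000 line goes further. On its plain wording, an admission value alone satisfies it, whatever happens after study drug.

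Late and staggered presenters are the likeliest to arrive abnormal, and the protocol's rationale (2.3 and 3) points to late presentation as the setting where PP100-01 might add to NAC. In groups of 6 and 2, one such patient can account for a whole between-arm difference.

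**Working it through.** **Inputs.** Three cohorts of 6 + 2 (Protocol 6.6.1): 3 × (6 + 2) = 24, which reproduces the stated total, with 18 on PP100-01 and 6 on NAC alone. The plan has no power calculation to reproduce. Intervals are two-sided 95% (SAP 3.2); Clopper-Pearson is used here for the exact interval.

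**Weight of one patient who enters above a threshold and stays above**
- Dose group or pooled NAC alone: 1/6 = 16.7 points.
- NAC-alone pair within a cohort: 1/2 = 50 points.

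**What the table would show.** Suppose that one of 6 enters above ALT 100 and stays above, and nobody else crosses.
- As written: 1/6 = 16.7% (0.4% to 64.1%).
- Among patients at or below 100 before the bolus: 0/5 = 0% (0% to 52.2%).
- The same patient in a NAC-alone pair, as written: 1/2 = 50% (1.3% to 98.7%).

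**How often.** The documents give no share of patients above a threshold at entry. The historical figures in Protocol 2.2.1 (94/1270 = 7.4% with ALT>1000; 233/1270 = 18.3% with ALT>100) are post-treatment rates and cannot stand in for it. So the share p is an assumption, taken as equal and independent across groups. P(at least one of n) = 1 − (1 − p)^n. P(unequal entry counts, 6 v 6) = 1 − Σ b(k)², where b(k) is the Binomial(6, p) probability of k.

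| Assumed p | ≥1 in a group of 6 | ≥1 in a pair | ≥1 in all 24 | Dose group and pooled NAC unequal at entry |
|---|---|---|---|---|
| 2% | 11% | 4% | 38% | 20% |
| 5% | 26% | 10% | 71% | 40% |
| 10% | 47% | 19% | 92% | 58% |
| 20% | 74% | 36% | 99.5% | 71% |

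The last column is closest to the problem but still overstates it for the 10 h and 20 h indicators, because a patient counts there only if still above the threshold at that time.

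**Mixing.** If 10% enter above and stay above, and 10% of the rest cross later (both assumed), the indicator reads 0.10 + 0.90 × 0.10 = 19.0%. Of the patients counted, 0.10/0.19 = 53% were above before PP100-01.

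**What already uses baseline**
- ALT: change from baseline, 50% rise and doubling at 10 h and 20 h, and individual profiles (SAP 4.5).
- INR: change from baseline and individual profiles, but no baseline-relative binary indicator.
- Both: a baseline summary by arm (SAP 4.2), but no cross-tabulation of threshold status against entry status. SAP 4.6 does plan that table for ECG.

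**Feasibility.** ALT and INR are taken at screening and at 2 h, just before PP100-01 (Protocol 7.1.1 and 7.2). The lay summary says that the pre-PP100-01 sample is obtained in all patients, so NAC-alone patients have a matching value.

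**The case against.** The strongest reply is that the SAP never calls these new-onset events. They are levels at a time, and levels have a role of their own: INR above 1.3 is among the criteria in Protocol 7.1.8 for the decision on further NAC, and Protocol 2.2.1 describes ALT>1000 as the conventional definition of severe hepatotoxicity. Reporting levels in all patients beside relative measures is legitimate. The patient falling from 400 to 250 would appear as a fall in the change analysis and the profile, and as a non-event on the 50%-rise and doubling lines. Allocation is randomised within cohort, so entry status is balanced on average, and chance imbalance at 6 v 6 or 6 v 2 touches every outcome here. An interval of 0.4% to 64.1% would mislead few readers, and SAP 4.4 allows a fall-back to descriptive summaries. Restricting the denominator also has a price: it drops improving patients rather than crediting them, and at an assumed p of 15% each NAC-alone pair has a 1 − 0.85² = 28% chance of losing a member.

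Most of this stands. It is the reason to keep the all-patient proportions and make the restricted ones supplementary. It does not answer the open ALT>1000 window, the lack of a baseline-relative binary for INR, or the missing cross-tabulation.

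Two stronger readings are tempting. A reader might infer that the indicators favour one arm systematically; randomisation rules that out as an expectation. A reader might also take the chance of at least one affected patient among 24 (71% at p = 5%) as the chance of a distorted comparison. It is not: the share is assumed, the patient must still be above the threshold at 10 h or 20 h, and the arms must differ.

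**Conclusion.** The point holds as a gap in definition and presentation. The threshold indicators pool injury present before PP100-01 with injury that appears after it, and the ALT>1000 line can be met before any study drug is given. The size per patient is certain: 16.7 points in a group of 6 and 50 in a pair, provided that the patient stays above the threshold (for ALT>1000, an entry value is enough). How often this happens rests wholly on an entry prevalence that the documents do not give. The effect is noise and misclassification. The existing baseline-relative analyses cover much of it for ALT and less for INR. For exploratory secondary indicators in 24 patients, this is minor to moderate, and worth correcting because the correction needs no new data.

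**What to change.** In SAP 4.5:

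1. Count ALT>1000 only on samples taken after PP100-01, or after the matching 2 h time in NAC-alone patients.
2. Keep the all-patient proportions, and cross-tabulate each threshold indicator by arm against status on the last pre-bolus sample (the matching 2 h sample in NAC alone), as SAP 4.6 does for ECG. Show the number above the threshold at entry.
3. Add, as a supplementary line, new-onset proportions among patients at or below the threshold on that sample.

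Name that sample explicitly, because SAP 4.2 allows baseline values from three time points. The INR>1.3 line at 20 h is printed twice, with no 10 h line although Protocol section 4 lists one; that is a separate slip to correct at the same time.

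The cost is a few sentences of SAP text and a few lines of programming on values already collected. The downside is that the supplementary denominators shrink, and a NAC-alone pair may fall to 1 or 0, so that line should be read as description only.

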4.6 Safety Secondary Outcomes (Safety population)

Vital signs (systolic blood pressure, diastolic blood pressure, pulse, respiratory rate, temperature, oxygen saturation) and haematology and clinical biochemistry parameters (PT, alkaline phosphatase, bilirubin, creatinine, haemoglobin, urea, MCV, WBC, sodium, potassium) will be summarised and analysed at their measurement time points using methods corresponding to those described in Section 4.5.

The ECG result (Normal / Abnormal Not Clinically Significant / Abnormal Clinically Significant) will be summarised by treatment group and overall at 2.5, 10 and 20 hours. The ECG summary results at each of these time points will also be cross-tabulated against the baseline ECG result, by treatment group and overall.

The number and proportion of participants who have anaphylactoid reactions recorded will be summarised by treatment group and overall in the same manner as for the primary outcome analysis in Section 4.4.

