7.1.4 Physical examination

A baseline physical exam will be completed assessing the Cardiovascular, Respiratory and GI systems and this data recorded on the CRF. Any AEs/SAEs identified during the exam will be recorded/reported. Additional full physical examinations will be completed if AE/SAEs are reported, requiring a more thorough exam to be carried out. This will include assessment of local toxicity at the site of intravenous administration.

All new findings or changes to previous findings from vital signs or baseline physical exam considered clinically significant are to be recorded in the CRF, as an adverse event if the finding is made subsequent to the patient signing the ICF for the main study (See Section 11). If the patient has received a dose of study medication it should be deemed whether the AE is related or non-related to the study drug.

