7.1.6 ECG

An ECG will be performed on resting patients at baseline, 2.5hr, 10hr and 20hr and any clinically significant deviations recorded.

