3.2 General principles

In general terms, categorical data will be presented using counts and percentages, whilst continuous variables will be presented using the mean, standard deviation (SD), median, minimum, maximum and number of patients with an observation (n), using a format similar to example tables 1 and 2 below. Data will be summarised overall and split by PP100-01 treatment group (NAC alone; NAC + 2µmol/kg PP100-01; NAC + 5µmol/kg PP100-01; NAC + 10µmol/kg PP100-01) and timepoint, where applicable.

Example 1. Data presentation for categorical data

Variable	Timepoint	Category	NAC alone	NAC + 2µmol/kg PP100-01	NAC + 5µmol/kg PP100-01	NAC + 10µmol/kg PP100-01	Overall
			N=xx	N=xx	N=xx	N=xx	N=xx
Variable A	Timepoint x	Category 1	xx (%)	xx (%)	xx (%)	xx (%)	xx (%)
	
		Category n	xx (%)	xx (%)	xx (%)	xx (%)	xx (%)

Example 2. Data presentation for continuous data

Variable	Timepoint / visit	Statistic	NAC alone	NAC + 2µmol/kg PP100-01	NAC + 5µmol/kg PP100-01	NAC + 10µmol/kg PP100-01	Overall
			N=xx	N=xx	N=xx	N=xx	N=xx
Variable A	Timepoint x	Mean (SD)	Xx	xx	xx	Xx	xx
		Median	Xx	xx	xx	Xx	xx
		Min, Max	xx, xx	xx, xx	xx, xx	xx, xx	xx, xx
		n	Xx	xx	xx	Xx	xx

Two-sided 95% confidence intervals (CIs) will be presented.

Where there are missing data for an outcome variable, in the first instance, a complete case analysis will be performed for that outcome, unless otherwise specified. In tabulations, numbers of missing observations will be provided, but percentages will not include them.

Normality will be examined by normal probability plots. If the distributional assumptions for the parametric approach are not satisfied, further data transformation (to alleviate substantial skewness or to stabilise the variance), or other suitable methods will be considered. This will be documented in the statistical results report together with the reasoning supporting the action taken, if applicable.

All analyses and data manipulations will be carried out using SAS [1].

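### SAP 4.6 plans no patient-level count or baseline shift table for safety laboratory values and vital signs, and SAP 4.9 plans no listing of them

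*SAP*

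**What the plan says.** SAP 4.6 names six vital signs (systolic and diastolic pressure, pulse, respiratory rate, temperature, oxygen saturation) and ten laboratory parameters (PT, alkaline phosphatase, bilirubin, creatinine, haemoglobin, urea, MCV, WBC, sodium, potassium). They "will be summarised and analysed at their measurement time points using methods corresponding to those described in Section 4.5".

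For continuous markers, SAP 4.5 gives group means with 95% intervals and differences in means. The comparisons are with the NAC-alone patients of the same cohort and with all NAC-alone patients combined. It repeats these for change from baseline. It also plans a panel of plots per group: "Each will show the profile of the measurements for individual patients overlaid by the treatment group mean profile". SAP 3.2 adds median, minimum and maximum. The proportions of patients beyond a limit in SAP 4.5 concern paracetamol, ALT and INR only.

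ECG is treated differently. It is a three-level category, and "The ECG summary results at each of these time points will also be cross-tabulated against the baseline ECG result".

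On adverse events, protocol 7.1.4 says that "changes to previous findings from vital signs or baseline physical exam considered clinically significant are to be recorded in the CRF", as an adverse event once consent has been signed. It does not mention laboratory results. Protocol 7.1.6 asks for ECGs to be done and "any clinically significant deviations recorded", without saying whether that means as an adverse event.

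On listings, the safety-population paragraph of protocol 12.2, reproduced in SAP section 2, promises that all patients' data will be listed. SAP 4.9 lists exclusions, withdrawals, medical history, adherence, deviations, adverse events and concomitant medication. It lists no laboratory, vital-sign or ECG data.

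**The concern.** The trial is a phase 1 safety study with six patients per dose. A safety signal at that size is likely to be one or two individuals, not a shift in a mean of six. The useful questions are how many patients moved from normal to abnormal, in which group, and who they were. For ECG the SAP answers the first two. For the sixteen parameters in SAP 4.6 it answers none of them, because no limit is stated and no listing is planned.

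The gap matters most for laboratory values. A vital-sign change judged clinically significant reaches the adverse event tables through protocol 7.1.4. No equivalent sentence covers a laboratory change, so whether it appears anywhere as a patient-level event depends on the investigator's unguided judgement.

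**Working it through.** **Inputs.** Each cohort has 6 patients on PP100-01 plus NAC and 2 on NAC alone (protocol 6.6.1). Three cohorts give 3 × (6 + 2) = 24 patients, as stated, and 3 × 2 = 6 combined NAC-alone controls. Intervals are 95% and two-sided (SAP 3.2). Protocol 12.3 gives no power or precision figure to reproduce. The SAP does not name the interval method; the usual t interval with pooled variance is assumed here.

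**One patient changes by D and the others do not.** The group mean moves by D/6. The same patient also inflates the variance: the sum of squares about the mean is D²(1 − 1/6) = 5D²/6.

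| Comparison | Variance estimate | Standard error | t | Critical value |
|---|---|---|---|---|
| Within the group of 6 | (5D²/6)/5 = D²/6 | √(D²/6 × 1/6) = D/6 | 1.00 | 2.57 |
| Against 6 controls | (5D²/6)/10 = D²/12 | √(D²/12 × (1/6 + 1/6)) = D/6 | 1.00 | 2.23 |
| Against 2 controls | (5D²/6)/6 = 5D²/36 | √(5D²/36 × (1/6 + 1/2)) = 0.304D | 0.167/0.304 = 0.55 | 2.45 |

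D cancels, so no single change, however large, brings the interval away from zero. On the log scale D becomes a log ratio and the algebra is the same. With unequal variances and unchanged controls the standard error is again D/6, so t = 1.00 on 5 degrees of freedom (critical value 2.57).

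**With ordinary variation in everyone.** Simulation of 40,000 runs, assuming normal data with equal SD, with one patient in six shifted. The table shows how often the 95% interval excludes zero in the direction of the shift. With no shift this would be 2.5%.

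| Shift in one patient | Within group | Against 2 | Against 6 |
|---|---|---|---|
| 3 SD | 2.7% | 1.2% | 4.0% |
| 5 SD | 0.6% | 0.1% | 2.0% |
| 10 SD | 0.0% | 0.0% | 0.1% |

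The chance of a flag falls as the change grows.

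**Illustration with assumed values.** Creatinine is 70 in five patients and 210 in one. The mean is 93.3, the median 70, the geometric mean 84 and the maximum 210. Against six controls all at 70 the difference is 23.3 with standard error 23.3. The interval is 23.3 ± 2.228 × 23.3, or −28.7 to 75.3. The maximum of 210 would be printed. The tables would not say which patient it was, what that patient's baseline was, or whether a second patient was also out of range.

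**What a count would add.** One patient in six would be reported as 1/6 (16.7%), exact 95% interval 0.4% to 64.1%. For 0/6 the interval is 0% to 45.9%. At assumed true rates of 5%, 10% and 20%, the chance that at least one of six shows the change is 26%, 47% and 74%. The count records the event, but the intervals are too wide to separate groups.

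**The case against.** A reader might infer that an abnormal patient is averaged away. The documents do not support that. SAP 4.6 takes over the individual profile plots of SAP 4.5, and SAP 3.2 requires minimum and maximum, so an outlier is on display.

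A reader might also infer that a marked blood-pressure fall would escape patient-level analysis. It would not, if judged clinically significant. Protocol 7.1.4 makes it an adverse event, and SAP 4.4 and 4.9 count adverse events per patient with exact intervals and list them.

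A third tempting step is to call for analysis of ECG intervals. The documents do not show that intervals are captured. ECG already has a shift table, and protocol 2.3 does not name an ECG effect among the important potential risks. That request is a preference and is not part of this point.

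The laboratory route is not wholly empty either. The adverse event definition in protocol 10.2 is broad, and 10.3 says to record doubtful clinical observations. ALT, INR and paracetamol already have patient-level proportions. The safety committee reviews each cohort and may request further analyses (protocol 10.10), so escalation does not rest on the SAP 4.6 tables. Finally, counts out of six will not separate groups statistically.

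All of this stands and limits the size of the point. It does not supply a count, a baseline classification or a patient listing for the SAP 4.6 parameters, and it does not reconcile SAP 4.9 with protocol 12.2.

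**Conclusion.** The point holds as a cheap improvement to the safety reporting. For ten laboratory parameters and six vital signs, the only planned between-group comparison is one of means. With six patients per dose it cannot flag a single affected patient: t tends to 1.00 against six controls and 0.55 against two, below the critical values of 2.23 and 2.45. An outlier is visible in plots and extremes but not counted, classified against baseline or identified. SAP 4.9 also falls short of the listing promised in protocol 12.2.

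The t limits assume a pooled t interval and one affected patient; they need no assumption about the SD. The simulated percentages assume normal data with equal SD, and the creatinine values and event rates are illustrative. The result does not show that any event would go unrecorded, and it does not touch the primary outcome analysis.

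**What to change.** **SAP 4.6.** Extend the baseline cross-tabulation already planned for ECG to each of the ten laboratory parameters and six vital signs. Tabulate the worst category (low, normal, high) after the bolus against the baseline category, with patient counts by treatment group. For NAC-alone patients use the same scheduled times, that is 2.5, 10 and 20 hours for vital signs and 10 and 20 hours for laboratory values. Use the laboratory reference range, or limits set in advance by the clinical team, and name the sample that serves as baseline. Report the counts descriptively.

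**SAP 4.9.** Add patient listings of laboratory, vital-sign and ECG data, ordered by treatment group, patient and time point, with out-of-range values flagged. This brings the SAP into line with protocol 12.2.

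**Secondary, at the next protocol amendment.** State in protocol 7.1.4 and 7.1.6 that clinically significant laboratory and ECG changes are handled for adverse event recording in the same way as vital-sign changes. This is mainly a clarification.

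**Cost.** The SAP changes use data already collected. They need more tables and an agreed list of limits, but no new procedure, sample or patient. The protocol sentence needs the ethics, regulatory and local approvals described in protocol 16.1, so it is best added to an amendment made for other reasons.
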